7.6 REQUIRED EVALUATIONS

7.6.1 Medical and Safety Assessments:
			Time Points [#]		
	Screening	Baseline (Visit 1)	7-10 days post-infusion	6 months	12 months
CBCD*, CMP*, participant HLA, fragile X, CMA/WES	х				
Review of prior records ± videos	Х				
History & Physical		Х		Х	
Samples for storage of DNA & viable mononuclear cells, DNA extract and hold		х			
Donor Referral Panel		Х			
CBCD, CMP, HLA Antibody Screen (PRA), Immune Reconstitution Panel, Humoral Immune Profile		X*		х	х
Neuropsychological evaluation		Х		Х	Х
Safety Assessment –in person (Day post-infusion)		х			
Safety Assessment – phone call/survey			Х		

*CBCD, CMP, PRA may be obtained at initial visit or within 6 months prior to consent; HLA, fragile X, CMA/WES any time prior to enrollment. Safety and return assessments should be performed within a month of the indicated time point.

7.6.2 Diagnostic, Behavioral, Cognitive/Language, and Attention evaluations.

	Measure	Time (min)	Baseline	3 mo.	6 mo.	9 mo.	12
Clinician	Brief Observation of Symptoms of	45-60	Х				
Assessme	Autism (BOSA)						
nt w/ Child	Developmental Assessment of Young	45-60	Х				
	Children – Second Edition (DAYC-2)						
Other							
Assessme							
nts w/	SenseToKnow (S2K) app	10	Х		Х		
Child	Demost Ohild latens sting (DOI) for JEDI	40	V		X		
Observatio n of child	Parent-Child Interaction (PCI) for JERI	12	Х		Х		
n of child	rating						
Caregiver	Vineland Adaptive Behavior Scales,	60-120	Х		Х		Х
Interviews	Third Edition Survey Interview Form	00-120	^		^		^
interviews	Clinical Global Impression Parent	30-45	Х		Х		
	Interview	30-43	X				
-	Medical/Behavioral History	15-30	Х	Х	Х	X	Х
	Questionnaire (MBHQ)	10 00	~				
Caregiver	Pervasive Developmental Disorder	30-45	Х	Х	Х	Х	Х
Questionn	Behavior Inventory (PDDBI)						
aires	Intervention History	15	Х	Х	Х	Х	Х
(Conducte	MacArthur-Bates Communicative	20-40	Х	Х	Х		Х
d with the	Development Inventories, Second						
Caregiver	Edition (CDIs)						
Only)	COVID-19 Exposure and Family	15	Х	Х	Х	Х	Х
	Impact Survey (CEFIS)						
	Pediatric Quality of Life (PedsQL)	5-10	Х		Х		Х
	Demographic Form	10	Х				
	Clinical Global Impression – Severity	15	Х		Х		
	(CGI-S)						
	Clinical Global Impression –						
	Improvement (CGI-I)						
Other	Diagnostic Statistical Manual-5 (DSM-	3-5	Х				
Clinician	5) Checklist						
Completed		0.5	X		X		
	Clinical Global Impressions - Severity	3-5	Х		Х		

Clir	nical Global Impressions -	3-5		Х	
Imp	provement				

8.0 STATISTICAL CONSIDERATIONS

8.1 STUDY DESIGN

This is a single site, Phase I, prospective study of intravenous hCT-MSC infusion in 12 children 18 months to <4 years (3 years 364 days) of age with ASD. All participants will be treated with hCT-MSC. Participants will receive a single hCT-MSC infusion at baseline and evaluated at 6 (in person) and 12 (remotely) months post-infusion. Duration of study participation will be 12 months from the time of the first infusion.

8.2 STUDY DURATION

Research participants will be enrolled in the study for 12 months after the administration of the hCT-MSC infusion.

8.3 DEMOGRAPHICS AND BASELINE CHARACTERISTICS

Demographics and baseline characteristics will be summarized for all research participants. Characteristics to be examined include age, sex, race/ethnicity, IQ, and baseline behavioral status.

8.4 SAMPLE SIZE AND POWER CALCULATIONS

The proposed trial is an open label Phase I trial of one intravenous infusion of hCT-MSC in toddlers 18 months to <4 years (3 years 364 days) of age with a diagnosis of ASD. The primary outcome is safety, as measured by the incidences of infusion reactions, infections, and new-onset clinically significant anti-HLA antibodies. Efficacy measures will also be assessed. The primary efficacy measure is coded time spent in sustained engagement with the caregiver in a brief semi-structured parent child interaction task (PCIT). The change on this outcome measure from Baseline to Month 6 will be analyzed.

8.5 PRIMARY ENDPOINTS

The primary outcome is safety. Safety endpoints will include the incidence of infusion reactions, infections, and new-onset clinically significant anti-HLA antibodies. Presence of infusion reactions and infections will be assessed in person at the time of infusion, 24 hours after infusion, and at six months and will be assessed remotely at 7-10 days post-infusion and 12 months and will be reported descriptively. Anti-HLA antibodies will be assessed at six and 12 months post-infusion.

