A total of 66 non-serious Adverse Events (AEs) that were not specifically attributed to the study product were reported among 11 of the 12 enrolled participants (Figure 6). All of these reported events were Mild. The most frequently occurring event, agitation during the infusion procedure, was associated with the requirements of placing and maintaining an IV and being confined to a hospital room for the infusion, and all of these events resolved on the same day. A total of 22 other psychiatric or behavioral symptoms were reported in 7 different participants: 2 participants/2 events in Cohort 1, 1 participant/5 events in Cohort 2, and 4 participants/15 events in Cohort 3. These symptoms included aggression (n=2), agitation (n=5), anxiety (n=3), defiant behavior (n=2), depression (n=1), emotional labiality (n=1), insomnia (n=3), intentional self-injury (n=1), and stereotopies (n=4). Of note, 3 participants accounted for 17/22 of the psychiatric or behavioral adverse events. Aside from agitation during the infusion procedure, there was a trend of increasing frequency of non-serious adverse events with increasing number of doses administered, but this was not statistically significant. There were no differences observed in the frequency of AEs according to lot number (GMP-075: median=9 events/participant, range: 1-12; GMP-087: median=4.5, range: 0-13; GMP-088: median=3.5, range: 3-50) (P_{Kruskal-Wallis}=0.58). There were no concerning changes in blood counts, chemistries, basic inflammatory markers (CRP, ESR), or humoral and cellular immune profiles throughout the study. All participants remained Coombs negative.

Six months after the initial hCT-MSC dose, development of anti-HLA class I antibodies was observed in 5 of 9 participants who did not have detectable HLA antibodies pre-treatment. HLA antibody data is available on all 12 participants at baseline and 6 months, and 11/12 participants at ≥12 months after their final hCT-MSC dose. In those participants who developed new HLA antibodies by six months, the HLA antibodies persisted at ≥12 months (figure 7). The HLA antibodies were directed against HLA alleles/antigens expressed on the MSCs and not by the patient. There were no associated clinical events in patients who developed anti-HLA antibodies.

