2.9 RISKS AND BENEFITS

Potential risks associated with infusion of MSCs include a reaction to the product (rash, shortness of breath, coughing, wheezing, difficulty breathing, hypotension, hypertension, hypoxia, swelling around the mouth, throat or eyes, tachycardia, bradycardia, diaphoresis), transmission of infection, and HLA sensitization. Theoretical risks that must be considered but have not been associated with MSC administration in humans include the possibility of immune suppression and ectopic tissue formation. Cord blood collected with the cord tissue used to manufacture hCT-MSC is screened for infection, and the product must meet release criteria prior to infusion, as described below. Participants will not receive immunosuppressive therapy prior to or after infusion of hCT-MSC cells. Additionally, an inherent risk in completing study procedures in person is possible exposure to COVID-19; however, social distancing, screening, masking, cleaning and other safety procedures in line with the most recent guidelines from Duke Health and the Duke University School of Medicine have been implemented to minimize this risk as much as is feasible.

Potential benefits of this intervention include the possibility that hCT-MSC may, via direct or indirect mechanisms, induce changes that result in the reduction of the participant's core ASD symptomatology and improvement in abilities affected by ASD symptoms.

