4.0 STUDY DESIGN

4.1 GENERAL DESIGN

This is a single site, phase I, open-label, prospective study of one intravenous infusion of human umbilical cord tissue-derived mesenchymal stromal cells (hCT-MSC) in 12 toddlers \geq 18 months to <4 years (3 years 364 days) of age with autism spectrum disorder (ASD). All participants will receive a single intravenous dose of 2x10⁶ hCT-MSC per kilogram at baseline. The primary outcome is safety, as measured by the incidences of infusion reactions, infections, and new-onset clinically significant anti-HLA antibodies. The main clinical outcome measure is the change in social communication abilities from baseline to 6 months based on the Joint Engagement Rating Inventory (JERI).⁹¹ Duration of study will be 12 months from the time of the initial infusion.

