4.2 STUDY FLOW CHART

4.3 STUDY ENDPOINTS

Safety Endpoints:

Safety of hCT-MSC infusion in children with ASD will be assessed by:

- 1. Incidence and severity of infusion reactions
- 2. Incidence and severity of product-related infections
- 3. Evidence of alloimmunization via anti-HLA antibodies
- 4. Incidence and severity of graft vs. host disease
- 5. Incidence and severity of unexpected adverse events, by relation to study product

Efficacy Endpoints:

The primary clinical outcome measure is the change in social communication abilities from baseline to 6 months based on total score (1-7) on the Joint Engagement Rating Inventory (JERI), a commonly-used and well-validated coding system for rating the quality and quantity of social communication skills in toddlers with and without ASD.⁹¹

Change measured on the following endpoints from baseline to six months will be compared:

- 1. PDD Behavior Inventory Autism Composite Score (PDDBI)
- 2. Mean of the Socialization Subscale and Communication Subscale standard scores on the Vineland Adaptive Behavior Scales (VABS-3)
- 3. Clinical Global Impression Scale (CGI) Severity and Improvement (Improvement at 6 months only

4. Communicative Development Inventories (CDI-2): Words & Sentences subscales

Exploratory Endpoints:

Change measured from baseline to six months will be evaluated on the following outcome measures.

- 1. Changes in auditory orienting, facial expressions, look duration, attention to social and nonsocial stimuli, postural sway, and vocalizations as measured via computer vision analysis by an app that elicits and records autism symptoms on an iPad (SenseToKnow)
- 2. PDD Behavior Inventory (PDDBI) Subscales
- 3. VABS-3 Socialization Subscale Standard Score and age equivalent
- 4. VABS-3 Communication Subscale Standard Score and age equivalent
- 5. VABS-3 Daily Living Subscale Standard Score and age equivalent
- 6. VABS-3 Adaptive Behavior Composite Standard Score and age equivalent
- 7. Pediatric Quality of Life Scale Generic Core

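### The reference PRA for the new-onset anti-HLA endpoint may be up to 6 months older than consent, with no repeat required before infusion, so earlier antibody could be attributed to the product

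*Combined protocol and SAP*

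**What the plan says.** **Endpoint.** Section 8.5 states: "Safety endpoints will include the incidence of infusion reactions, infections, and new-onset clinically significant anti-HLA antibodies". Section 8.4 states: "The primary outcome is safety, as measured by the incidences of infusion reactions, infections, and new-onset clinically significant anti-HLA antibodies". Section 4.1 uses the same restriction, "new-onset clinically significant anti-HLA antibodies". The protocol summary keeps the clinical-significance qualifier but does not say new onset. The safety list in 4.3 has no qualifier: "Evidence of alloimmunization via anti-HLA antibodies". Section 8.5 adds that anti-HLA antibodies are assessed at 6 and 12 months.

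**Reference sample.** Section 6.6 asks for a PRA before treatment and at 6 and 12 months, with no limit on how old the first one may be. The 7.6.1 table places the PRA at baseline, 6 and 12 months. Its footnote allows CBCD, CMP and PRA to be taken either at the initial visit or during the 6 months before consent.

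**Why antibody is expected to matter.** Section 2.9 lists among the risks "transmission of infection, and HLA sensitization". For the prior hCT-MSC study, section 2.6 reports that "development of anti-HLA class I antibodies was observed in 5 of 9 participants who did not have detectable HLA antibodies pre-treatment", and that "The HLA antibodies were directed against HLA alleles/antigens expressed on the MSCs and not by the patient". It also says that no clinical events accompanied these antibodies.

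**The concern.** A new-onset endpoint is only as good as its zero point. If the negative reference sample was taken months before exposure, the interval being tested includes time before the child received any product. A conversion in that time looks the same, on a later PRA, as one caused by the infusion. The trial has a single arm, so no control group would show how many conversions occur without the product. The error would inflate the rate attributed to hCT-MSC.

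There is a second, lesser problem. Whether a given antibody enters the primary figure depends on the words *clinically significant*, for which the available text gives no assay cut-off, strength threshold, specificity rule, required clinical event or adjudicator. CTCAE v5.0, named in 9.1, grades adverse events and is not tied to this endpoint. With about a dozen children, one classification visibly changes the result.

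**Working it through.** **1. Figure to reproduce.** There is none. Section 8.4 gives no sample size, precision or error-rate calculation for this endpoint, and 8.5 is descriptive.

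**2. Age of the reference sample.** Inputs: up to 6 months before consent (7.6.1 footnote); consent obtained at the baseline visit (7.1); first follow-up PRA at 6 months (6.6, 8.5); window of one month (7.6.1).
- Pre-infusion exposure in the tested interval: up to 6 months, plus any gap from consent to infusion.
- Reference PRA to 6-month PRA: 6 + 6 = 12 months, or 12 + 1 = 13 with the window.
- If *consent* meant the separate screening consent (5.4, 7.1, 7.2), the gap could be longer.

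**3. Size per misclassified child.** With the denominator N held fixed, one child shifts the figure by 1/N.
- N = 12 (every enrolled child PRA-negative): 1/12 = 8.3 points. Exact 95% CI for 1/12 is 0.2% to 38%, against 0% to 26% for 0/12.
- N = 9 (the number negative in the prior study, assumed here): 1/9 = 11.1 points. Exact 95% CI for 1/9 is 0.3% to 48%, against 0% to 34% for 0/9.
- If correct classification would also remove the child from the at-risk set, and k other children convert, the shift is (k+1)/N − k/(N−1) = (N−1−k)/[N(N−1)]. This equals 1/N at k = 0 and is smaller otherwise. For example, with N = 12 and k = 5, 6/12 − 5/11 = 50.0% − 45.5% = 4.5 points. So 8 to 11 points is the upper end.

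**4. How often.** The documents give no rate q of new antibody in the pre-infusion gap. As an assumed range, if all N children used an early sample, the chance of at least one misclassification is 1 − (1−q)^N:

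| q (assumed) | N = 9 | N = 12 |
|---|---|---|
| 1% | 9% | 11% |
| 2% | 17% | 22% |
| 5% | 37% | 46% |
| 10% | 61% | 72% |

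The spread shows only that the answer depends on an unknown; it does not estimate it.

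**5. Effect of the undefined qualifier.** Inputs from 2.6: 9 children antibody-negative before treatment, 5 with new product-directed antibody, 0 with an associated clinical event. Clopper-Pearson 95% limits are the 0.025 quantile of Beta(x, n−x+1) and the 0.975 quantile of Beta(x+1, n−x). For x = 0 the lower limit is 0 and the upper limit is 1 − 0.025^(1/n).
- Product-directed antibody counts: 5/9 = 56% (21% to 86%).
- A clinical event is required: 0/9 = 0% (0% to 34%, from 1 − 0.025^(1/9) = 0.336).

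The intervals describe sampling error within each reading. The difference between the two figures is purely definitional.

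**The case against.** The strongest reply to the timing point is that the footnote is permissive. The PRA is scheduled at the baseline visit, 6.6 says pre-treatment, and the site may in practice draw every reference sample then. Prior cell therapy and IVIG are exclusions, and Appendix 1 asks about transfusion, both ever and in the past 2 months. Participant HLA typing would also help attribution. A toddler acquiring antibody in the gap may therefore be uncommon. This stands as a limit on likelihood: a reader might infer that the reference samples will be stale or that misattribution is expected, and the documents support neither. It does not remove the allowance. No repeat is required, and the available text does not commit this trial to the specificity testing that could resolve a doubtful case.

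On the definition, the reply is that 4.3 covers any alloimmunization and 8.5 schedules antibody assessment without the qualifier. That stands. A reader might infer that seroconversions without clinical events would go unrecorded; they would not. Nor is there a reason to demote the sponsor's chosen endpoint. What remains open is which count the primary figure represents.

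The prior 5/9 also needs care. That study had three cohorts, and 2.6 discusses non-serious adverse events by number of doses, whereas this trial gives one infusion. Persistence at 12 months or later rests on antibody data from 11 of 12 participants. The 5/9 shows that the definition matters; it does not forecast this trial.

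**Conclusion.** The timing point holds as a cheap improvement. As written, the plan permits a reference PRA up to 6 months before consent, so an antibody that predates infusion can be counted as new onset. The size is at most 8 points per child with 12 at risk, or 11 with 9 at risk; both denominators are assumptions, because the number PRA-negative at entry is not yet known. Frequency cannot be judged from the documents.

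The definition point holds as a secondary matter of reconciling 4.1, 8.4 and 8.5 with 4.3. On the prior study's data the choice of meaning alone moves the figure from 0% to 56%.

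A reader might go further and conclude that the trial's safety decisions are compromised. The documents do not support that: none of the stopping guidelines in 9.5 refers to anti-HLA antibody, and no hypothesis test or success threshold depends on it. The consequence is confined to how the primary safety figure is reported and attributed. The absence of a criterion and of a repeat PRA is established for the available text only.

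**What to change.** 1. **Reference sample (main change).** Amend the 7.6.1 footnote so that the reference PRA for this endpoint is drawn at the baseline visit, before infusion, and state the same in 6.6. Cost: at most one extra tube. That visit already includes stored DNA and cell samples, a donor referral panel and the immune panels, and the early-sample allowance names only CBCD, CMP and PRA.

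2. **Endpoint wording (secondary).** Reconcile the summary, 4.1, 8.4 and 8.5 with 4.3 by reporting two lines side by side: all new-onset anti-HLA antibody at 6 and 12 months, and the clinically significant subset. Give each as n/N with an exact 95% CI among children PRA-negative before infusion. The sponsor should fix the criteria in writing (assay, threshold and any clinical component) before the first 6-month result is known. Cost: wording in a few sections and one short definition. The broader line may look less favourable than the subset alone, which is a reason to show both.

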8.6 EFFICACY ENDPOINTS

Primary Endpoint:

The primary clinical outcome measure is the change in social communication abilities from baseline to 6 months based on total score (1-7) on the Joint Engagement Rating Inventory (JERI), a commonly-used and well-validated coding system for rating the quality and quantity of social communication skills in toddlers with and without ASD.⁹¹

Secondary Endpoints:

Change measured on the following endpoints from baseline to six months will be compared:

- 1. PDD Behavior Inventory Autism Composite Score (PDDBI)
- 2. Mean of the Socialization Subscale and Communication Subscale standard scores on the Vineland Adaptive Behavior Scales (VABS-3)
- 3. Clinical Global Impression Scale (CGI) Severity and Improvement (Improvement at 6 months only

4. Communicative Development Inventories (CDI-2): Words & Sentences subscales

Exploratory Endpoints:

Change measured from baseline to six months will be evaluated on the following outcome measures.

- 1. As measured by an app that elicits and records autism symptoms on an iPad (SenseToKnow), changes in auditory orienting, facial expressions, look duration, attention to social and nonsocial stimuli, postural sway, and vocalizations as measured via computer vision analysis
- 2. PDD Behavior Inventory (PDDBI) Subscales
- 3. VABS-3 Socialization Subscale Standard Score and age equivalent
- 4. VABS-3 Communication Subscale Standard Score and age equivalent
- 5. VABS-3 Daily Living Subscale Standard Score and age equivalent
- 6. VABS-3 Adaptive Behavior Composite Standard Score and age equivalent

9.0 SAFETY AND ADVERSE EVENT REPORTING

9.1 **DEFINITIONS**

Adverse Event (AE): An adverse event is any untoward medical occurrence associated with the use of the investigational product regardless of whether it is considered related to the investigational product.

Serious Adverse Event (SAE): An adverse event or suspected adverse reaction is considered "serious" if, in the view of either the investigator or sponsor, it results in any of the following outcomes: death, a life threatening adverse event, inpatient hospitalization or prolongation of existing hospitalization, a persistent or significant incapacity or substantial disruption of the ability to conduct normal life functions, or a congenital anomaly/birth defect. Important medical events that may not result in death, be life-threatening, or require hospitalization may be considered serious when, based upon appropriate medical judgment, they may jeopardize the participant and may require medical or surgical intervention to prevent one of the outcomes listed in this definition.

Grade/Severity: Grade/severity will be assessed according to CTCAE v5.0 guidelines.

Suspected Adverse Reaction: A suspected adverse reaction is any adverse event for which there is a reasonable possibility that the investigational product caused the adverse event. "Reasonable possibility" means there is evidence to suggest a causal relationship between the investigational product and the adverse event.

*Causality:* The investigator will use the following question when assessing causality of an adverse event to the investigational product: "Is there a reasonable possibility that the investigational product caused the event?" An affirmative answer designates the event as a suspected adverse reaction.

9.2 ADVERSE EVENT REPORTING

All adverse events reported or observed during the study beginning at the time of the initial infusion must be recorded. AEs occurring in 5% of enrolled participants will be reported in clinicaltrials.gov. Information to be reported includes date when the site became aware of the event, investigator-specified assessment of severity and relationship to study therapy, whether there is an alternative etiology, seriousness, as well as any required treatment or evaluations, and

outcome. In general, investigators should report adverse events as diseases or syndromes whenever possible, instead of reporting individual component symptoms, signs, laboratory abnormalities, and sequelae.

Severe adverse infusion reactions (fatal, life-threatening or requiring hospitalization) will be reported within seven calendar days of receipt of the information. All fatal or life threatening SAEs will be reported by the investigator or its representatives to the FDA by telephone or fax within seven calendar days after receipt of the information, following FDA guidelines. All serious and unexpected AEs will be reported to the FDA via a written report within 15 days of receipt of the information (21 CFR 312.32). If the principal investigator assesses an event to be unrelated to the study, then the event will not require expedited reporting but will be included in the annual summary report.

The following events within 24 hours of hCT-MSC infusion will also be recorded in the e-CRF: infusion reaction, sinus bradycardia, sinus tachycardia, hypertension, hypotension, fever, rigors/chills, nausea, vomiting, infection, dyspnea, hypoxia, and hemoglobinuria.

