5.5 EARLY WITHDRAWAL OF RESEARCH PARTICIPANTS

Criteria for Removal from Protocol Therapy:

- 1. Diagnosis of a genetic disease while under evaluation or on study.
- 2. Change in medical condition that precludes study participation.

Patients who are off protocol therapy are to be followed until they meet any one of the off-study criteria (see below). Follow-up data will be obtained on off-protocol participants unless consent is withdrawn. Participants that are taken off study prior to infusion of hCT-MSC will be considered not evaluable and can be replaced with another participant.

Off-Study Criteria:

- 1. Death.
- 2. Lost to follow-up.
- 3. Withdrawal of consent for any further data collection.
- 4. Completion of the final study visit.

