6.5 ADMINISTRATION OF PRODUCT

Patients will be admitted to the infusion center on the day of their scheduled infusion. Patients may require some sedation prior to the IV placement if they are unable to remain still or cooperate. A peripheral IV will be placed by clinical or study staff. Patients will be premedicated with Benadryl 0.5mg/kg/dose IV and Solumedrol 0.5-1mg/kg IV. The hCT-MSCs or placebo product will be administered intravenously over 30-60 minutes. Vital signs (heart rate, blood pressure, temperature, respiratory rate) will be attempted upon arrival to the clinic and monitored as clinically indicated. Pulse oximetry will be monitored continuously throughout the infusion and for at least 5 minutes post infusion. Patients should be observed a minimum of 15-30 minutes post infusion.

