10.0 DATA SAFETY MONITORING BOARD (DSMB)

A DSMB will be formed and a charter established. Members of the DSMB will be independent of Duke University and comprised of a minimum of three members, including a clinician with experience in the treatment of ASD and a physician with experience in cell therapy. The DSMB will be notified immediately for all SAEs directly related to the study product throughout the study. A total safety assessment will be prepared on an annual basis and forwarded to the DSMB for review as well. The DSMB and its members will have the right to make decisions and act independently. Policies of the DSMB will be described in the DSMB charter and signed by all members.

All study related and unexpected SAEs reported or observed during the study beginning at the time of the study infusion must be recorded and maintained in the study participant's paper files. Severe adverse infusion reactions (fatal, life threatening or requiring hospitalization) will be reported to the IRB and FDA in accordance with HRPP policies.

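### Mandatory adverse-event recording starts at the infusion and is tied to the product, so harms confined to the study procedures before it need not be recorded

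*Combined protocol and SAP*

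**What the plan says.** **When recording starts.** Section 9.2: "All adverse events reported or observed during the study beginning at the time of the initial infusion must be recorded". Section 10.0 repeats the start for a narrower class: "All study related and unexpected SAEs reported or observed during the study beginning at the time of the study infusion must be recorded".

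**What counts as an event.** Section 9.1 defines an adverse event as "any untoward medical occurrence associated with the use of the investigational product", whether or not it is judged related. The causality question is "Is there a reasonable possibility that the investigational product caused the event". Neither mentions study procedures.

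**What comes before the cells.** Section 6.5: "Patients may require some sedation prior to the IV placement if they are unable to remain still or cooperate"; then "A peripheral IV will be placed by clinical or study staff". Sections 6.5 and 7.3 give every child IV premedication before the infusion, and 7.3 names anesthesia among those who may place the line. Consent is obtained earlier in the same baseline visit (7.1), so the child is already a participant.

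**What happens to a child who is not infused.** Section 9.6 allows further enrollment to make up for any enrolled child who goes untreated. Section 5.5: "Participants that are taken off study prior to infusion of hCT-MSC will be considered not evaluable and can be replaced with another participant". Neither section requires the reason to be reported.

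**What the study is for.** Section 1.0 names feasibility and safety; objective 1 in section 3.0 names safety and tolerability. The primary incidences in 4.1 and 8.5 are infusion reactions, infections and new-onset clinically significant anti-HLA antibodies.

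**The concern.** For a toddler, receiving this treatment means the line, the premedication, sedation if it is needed, and then the cells. A question about feasibility and tolerability covers that whole sequence, but the recording rule starts at its last step. A pre-infusion harm serious enough to end the attempt leaves a child who never reaches the point where recording becomes mandatory and who may be replaced. The report could then describe 12 treated children without mentioning a 13th in whom delivery failed, and still comply with the protocol. With so few children, one such case matters to anyone planning the next study.

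**Working it through.** The plan gives no design figure to reproduce: section 8.4 states no alpha, power or precision target, and 8.5 reports safety descriptively. The check is therefore mainly a comparison of the text, with a small illustration.

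**Step 1. Does any section require recording before the cells start?**

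| Section | What it covers | Reaches a harm confined to the pre-infusion steps? |
|---|---|---|
| 9.2, general rule | Events from the initial infusion onward | No |
| 9.2, 24-hour e-CRF list | Named signs around the hCT-MSC infusion | Not if the child is never infused. If the hours before are read in, only the listed signs are covered; agitation is not among them |
| 10.0 | Related and unexpected SAEs from the infusion onward | No |
| 9.1 | Events associated with use of the product | Doubtful if infused; no product use if not infused |
| 9.4 | Names data gathered over the whole study as AE sources | Sets no start date and relies on 9.1 |
| 9.5 | Any death triggers a safety review | Deaths only |
| 5.5 | Follow-up of children off protocol therapy | Follow-up data, but no AE-recording rule |

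None does so clearly. A harm that begins or persists after the cells start, including a delayed effect of sedation or premedication, is inside the window.

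**Step 2. Replacement.** The off-study criteria in 5.5 are death, loss to follow-up, withdrawal of consent and completion. A non-fatal reaction is none of these, so the child is off protocol therapy but still followed. The clearer route to replacement is 9.6, which needs only that an enrolled child was not treated.

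**Step 3. Illustration (assumed event).** Suppose one enrolled child is harmed before infusion, is not infused and is replaced, and no other child has such an event. Exact (Clopper-Pearson) 95% limits:

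- Current text, 12 treated children: 0/12 = 0%. The upper limit is 1 − 0.025^(1/12) = 26.5%, so the interval is 0 to 26.5%.
- All enrolled children counted: 1/13 = 7.7%, interval 0.2 to 36.0%.

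**Step 4. Registry threshold.** Section 9.2 sets it at 5% of enrolled children. 1/12 = 8.3% and 1/13 = 7.7% both exceed 5%, so one event crosses the line if it is recorded. The denominator counts enrolled children, but mandatory collection for the numerator begins only at infusion.

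**Step 5. Largest effect on any-AE incidence among treated children.** If an infused child's only event in 12 months falls before the cells, the incidence moves from k/12 to (k+1)/12, which is 1/12 = 8.3 percentage points. If the child has any other event, the shift is zero. In the earlier hCT-MSC study (2.6), 11 of 12 children had at least one non-serious event not specifically attributed to product, although that count includes procedural agitation.

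**Step 6. How likely is it?** The documents give no per-child risk. With assumed risk p, the chance of at least one event in 12 children is 1 − (1 − p)^12:

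| p | 1% | 2% | 5% | 10% |
|---|---|---|---|---|
| At least one in 12 | 11.4% | 21.5% | 46.0% | 71.8% |

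**The case against.** The strongest reply is that this is a product-safety study and that opening the AE window at first exposure to the product is a legitimate choice. A reaction to the cells, or sensitization by them, cannot precede them, so the primary incidences hardly move. That stands. It limits the point to feasibility and tolerability, which the protocol also names as aims.

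Several stronger readings are tempting, and the documents do not support them:

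- *Pre-infusion harms go unrecorded and appear nowhere in the results.* Section 9.2 says when recording becomes mandatory; it does not forbid earlier recording. Section 9.4 could prompt staff to note such an event, and the death trigger in 9.5 is not tied to the infusion. The supportable statement is that recording is not required.
- *Section 5.5 removes the harmed child from the data.* It keeps children who are off therapy in follow-up unless consent is withdrawn. Replacement under 9.6 adds a child; it does not delete one. The registry denominator also keeps the enrolled child.
- *Sedation is a study requirement.* It is conditional. IV placement and premedication are the steps specified for every child.
- *The earlier study shows that such events are lost.* Its most frequent event, agitation during the infusion procedure, "was associated with the requirements of placing and maintaining an IV" and with confinement to a hospital room. Maintaining the line and confinement continue during the infusion. Those events were captured, were mild and resolved the same day. The passage shows that procedural burden is real in these children, not that it goes missing.

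None of this supplies a rule that requires recording of a harm confined to the pre-infusion steps, or an account of why a child was not infused.

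**Conclusion.** The point holds as a limited gap that should be closed. Sections 9.2 and 10.0 start mandatory recording at the infusion, and 9.1 ties definition and causality to the product. Harms from IV placement, premedication or sedation that resolve before the cells start, or that lead to the infusion being abandoned, therefore need not be recorded, and an untreated child may be replaced without a reported reason.

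A reader might infer that the primary safety result is biased. It is not, to any material degree, because its three named incidences concern the product. What is weakened is the evidence on feasibility and tolerability.

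The size depends on an assumed event: 0/12 against 1/13 = 7.7% for one harmed and replaced child. The 8.3-point shift in any-AE incidence is a ceiling for a treated child with no other event, and any-AE incidence is not itself a named endpoint in 4.3. How often such an event would occur cannot be judged from the documents.

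**What to change.** 1. **9.2 and 10.0:** start AE and SAE recording at the first study procedure on the infusion day (sedation, IV placement or premedication, whichever comes first). Change both, or the SAE start stays at the infusion.
2. **9.1:** extend the definition to events associated with study procedures. Keep the product causality question and add a second one about procedures. Without this, a premedication reaction in an uninfused child would arguably still not be an adverse event. State which question governs expedited reporting.
3. **CRF:** flag each event as before or after the start of cells, so that product-related rates among infused children are unchanged.
4. **9.4:** align its whole-study wording with the new start.
5. **5.5 and 9.6:** require a listing of every enrolled but uninfused child, with the reason and any events, whether or not the child is replaced.

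The cost is a few sentences in the protocol, one CRF flag, one extra causality item and one listing. The downside is that a few more minor procedural events will be listed. Sample size, primary endpoints and clinical care do not change.
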